6.5. Primary, Secondary, and Supportive Estimands

Unless otherwise specified, a composite strategy will be used for categorical efficacy endpoints, as described in Section 6.5.1. A hypothetical strategy will be used for continuous efficacy endpoints, as described in Section 6.5.4.

6.5.1. Primary Estimand

The primary clinical question of interest is: What is the difference between LY3471851 and placebo in the target patient population, in achieving a successful response at Week 24 without violating concomitant medication rules?

The violation of concomitant medication rules for this study includes (i) initiating or increasing in dose of corticosteroids, antimalarial, or immunosuppressant, or (ii) using prednisone >10 mg per day (or equivalent) after Week 12.

The estimand for the primary objective is described by the following attributes:

- population: modified intent-to-treat population
- endpoint: SLEDAI-4 at Week 24
- how to account for ICES: A **composite estimand strategy** will be used. Participants with violation of concomitant medication rules will be considered as treatment failure, that is, a nonresponder, after the first occurrence of violation of concomitant medication rules.
- population-level summary: difference in response rate of SLEDAI-4 at Week 24 between LY3471851 and placebo, and
- rationale for estimand: the primary estimand strategy assumes that a participant, who violates concomitant medications, was not receiving sufficient benefits from study intervention. This estimand is free of confounding effects of increase in concomitant medication use. Under the primary estimand strategy, a participant is considered a SLEDAI-4 responder at Week 24 if both of the following are met:
 - ≥ 4 points reduction from baseline in SLEDAI-2K score at Week 24
 - no violation of concomitant medication rules prior to Week 24.

If either or both of these criteria are not met, a participant is considered as a SLEDAI-4 nonresponder at Week 24. Apart from the primary estimand strategy, missing data imputation is described separately in Section 6.11.

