8.1.1. Primary Efficacy Outcome Measure: SLEDAI-4

The primary efficacy endpoint is the proportion of participants who achieve a SLEDAI-4 response at Week 24. A SLEDAI-4 response is defined as a ≥ 4 -point reduction in Systemic Lupus Erythematosus Disease Activity Index 2000 (SLEDAI-2K) score from baseline. To be considered a SLEDAI-4 responder, participants must complete the 24-week treatment period and comply with concomitant medication rules (Section 9.4.1). Section 4.2 provides the rationale for the selection of SLEDAI-4 as the primary efficacy measure.

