9.4. Statistical Analyses

9.4.1. General Considerations

CCI Unless other indicated in the SAP, the analyses will be conducted as follows:

- Primary and secondary endpoint analyses will be tested at a 2-sided α level of 0.05 for frequentist analyses.
- The primary estimand that will be used to analyze primary and secondary endpoints is a composite response estimand where comparisons will not include data collected after

intercurrent events of changes to background therapies or discontinuation. Participants who discontinue treatment prior to 24 weeks or who are noncompliant with concomitant medication rules are defined as nonresponders. Endpoint definition effectively gives complete data which will be analyzed as described in Section 9.4.2 and Section 9.4.3.

- No adjustments for multiplicity will be performed.
- Efficacy and PRO analysis models may contain the independent variables such as treatment group, baseline disease activity, and geographic region.
- Missing data for dichotomous responder endpoints will be imputed using the nonresponder imputation (NRI) method.
- Participants will be considered nonresponders for the NRI analysis if
 - they do not meet all the clinical response criteria
 - they are noncompliant with concomitant medication rules (Section 6.5)
 - they permanently discontinue study intervention at any time before the end of the treatment period for any reason, or
 - they are randomized and do not have at least 1 postbaseline observation.
- Mixed-effects model for repeated measures (MMRM) is the main method for analyzing continuous efficacy endpoints.
- Additional imputation methods may be considered for all endpoint types.

Baseline will be defined as the last available value before the first dose of study intervention for both efficacy and safety analyses. In most cases, this value will be what is recorded at the randomization visit (Visit 2). Change from baseline will be calculated as the visit value of interest minus the baseline value. For the post-treatment Follow-up Period, the baseline is defined as the last nonmissing assessment on or prior to entering the post-treatment Follow-up Period, that is, on or prior to the Week 24 visit, or the early termination visit (including ETV).

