4.1. Primary Objective

Objectives	Endpoints/Estimands

 To determine whether treatment with LY3471851 Q2W is superior to placebo in reducing the signs and symptoms of SLE as measured by SLEDAI-4 	
 The study will compare LY3471851 with placebo in participants with SLE. The primary comparison of interest is the difference in proportion of participants who achieve SLEDAI-4 response at Week 24. The primary comparison will be assessed using a composite estimand where the intercurrent events of premature discontinuation and use of prohibited medication are part of the response definition.

Abbreviations: Q2W = every 2 weeks; SLE = systemic lupus erythematosus; SLEDAI-4 = a ≥ 4 -point reduction in SLEDAI-2K score from baseline; SLEDAI-2K = Systemic Lupus Erythematosus Disease Activity Index 2000.

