the interaction of baseline value-by-visit as fixed factors. An unstructured covariance matrix will be used to model the within-patient variance-covariance errors. If this analysis fails to converge, the following structures will be tested in this pre-specified order: 1) heterogeneous Toeplitz, 2) heterogeneous autoregressive, 3) heterogeneous compound symmetry, 4) Toeplitz, 5) autoregressive), and 6) compound symmetry. The first covariance structure that converges using this prespecified order will be used. The Kenward-Roger method will be used to estimate the degrees of freedom. Type III sums of squares for the LS means will be used for the statistical comparison. The LS mean for each treatment group along with the estimate of the difference between treatments (difference between each LY3471851 dose group and placebo), standard error, p-value, and the 95% CIs will be reported at each visit along with p-values. For variables that are not collected at each postbaseline visit, data may exist at visits where the variable was not scheduled to be collected, due to early discontinuation visits. In these situations, data from the early discontinuation visit that do not correspond to the planned collection schedule will be excluded from the MMRM analyses (Andersen and Millen 2013). However, the data will still be used in other analyses.

When ANCOVA is used for efficacy/Health Outcomes measures, the model will include treatment, baseline score, baseline disease activity (SLEDAI-2K <10 ; SLEDAI-2K ≥ 10), corticosteroid dose at baseline (<10 mg/day or ≥ 10 mg/day), and geographic region as fixed factors. Type III sums of squares will be used. Differences in LS means between treatment groups will be displayed, with the p-value associated with the LS mean comparison to placebo (for each LY3471851 dose group) along with the 95% CI of the LS mean difference also provided. In addition to the LS means and tests, mean, SD, minimum, first quartile, median, third quartile, and maximum will be displayed.

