6.4. Definition of Baseline and Postbaseline Measures

Baseline will be defined as the last available value before the first dose of study drug for both efficacy and safety analyses, unless otherwise specified. In most cases, this will be the measure recorded at Week 0 (Visit 2). The treatment period starts after the first study drug administration and ends on one of the following:

- date of Visit 15 (Week 24) for patients who completed the treatment period
- for patients who discontinued treatment early
 - date of ETV, if ETV occurs less than 42 days after treatment discontinuation
 - date of the last visit that occurs less than 42 days after treatment discontinuation, if ETV occurs after 42 days since treatment discontinuation.

Change from baseline will be calculated as the visit value of interest minus the baseline value. Percent change from baseline will be calculated as 100 times change from baseline divided by baseline.

Postbaseline measurements are collected after study drug administration through Visit 15 (Week 24) or an early discontinuation visit. For electronic PROs related to efficacy assessments, unscheduled postbaseline visits that fall within the protocol-defined visit windows will be summarized in the by-visit analyses if there is no scheduled visit available. If more than 1 value is reported for the same scheduled visit, then the first value will be summarized in the by-visit analyses.

The Follow-up Period includes all visits that are 42 days or more after treatment discontinuation for patients who discontinue the treatment period early. For patients who complete the treatment period, the Follow-up Period includes Visit 801 for safety assessment. Randomized participants who were positive for anti-HBc at screening will have one additional posttreatment follow-up visit (Visit 802). The baseline value for the safety analysis of the posttreatment follow-up period is defined as the last nonmissing assessment prior to entering the posttreatment Follow-up Period, that is Week 24 (Visit 15) for treatment completers or last visit that occurred less than 42 days after treatment discontinuation for patients that discontinued treatment early. When the

Follow-up Period includes more than 1 visit, any safety analyses that are done for this period will only include the first visit of this period.

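### The SAP's composite responder rule leaves out treatment completion and relies on NRI, so a late discontinuer with an early termination value counted as Week 24 is not ruled out as a responder

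*SAP*

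**What the plan says.** SAP 4.1 sets the primary estimand as a composite in which "the intercurrent events of premature discontinuation and use of prohibited medication are part of the response definition". The protocol agrees. Under Protocol 8.1.1, to be a responder, "participants must complete the 24-week treatment period and comply with concomitant medication rules". Protocol 9.4.1 lists several separate grounds for nonresponse; one is that "they permanently discontinue study intervention at any time before the end of the treatment period for any reason". Having no postbaseline observation is a different item in that list, so the discontinuation item does not depend on data being missing. Protocol 9.4.2 repeats the rule for the primary analysis.

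SAP 6.5.1 puts the estimand into operation differently. It requires a drop of at least 4 "points reduction from baseline in SLEDAI-2K score at Week 24" and "no violation of concomitant medication rules prior to Week 24", and nothing else. The only intercurrent event it handles is the medication one: "Participants with violation of concomitant medication rules will be considered as treatment failure, that is, a nonresponder". SAP 6.14 and 6.15 repeat this for the primary and secondary endpoints.

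SAP 6.11 keeps missing data apart from the estimand strategy, names early treatment discontinuation as one cause of missingness, and defines NRI as acting on missing binary values. SAP 6.14 applies NRI to the primary analysis.

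**The concern.** NRI and a composite rule are not the same thing. NRI turns an absent value into a nonresponse; it leaves an observed value alone. The protocol's rule overrides an observed value once the participant has permanently stopped drug. If a discontinuer has a SLEDAI-2K score that the programming places at Week 24, the SAP counts a 4-point drop as a response and the protocol does not.

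At stake is the definition of the primary endpoint. SRI-4, BICLA and LLDAS take the same strategy through SAP 6.5.2 and 6.15. Two programmers working from the SAP could handle a late ETV differently and report different primary results.

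**Working it through.** **Step 1. Where the two rules differ.**

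- Completer: same result under both.
- Discontinuer with no value counted as Week 24: nonresponder by rule in the protocol, nonresponder by NRI in the SAP. Same result.
- Discontinuer with a value counted as Week 24, but a drop of under 4 points or a medication violation: nonresponder under both.
- Discontinuer with a value counted as Week 24, a drop of at least 4 points and no violation: nonresponder in the protocol, responder in the SAP. This is the only cell that differs.

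**Step 2. Can that cell be filled?** Protocol 7.1.1 gives a discontinuer an ETV and follow-up visits, not a Week 24 visit. The Schedule of Activities lists SLEDAI-2K at the ETV but not at Visits 801 or 802. So the value can come only from an ETV near Week 24.

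- Week 24 is Day 169 ± 3, that is Day 166 to 172.
- SAP 6.4 ends a discontinuer's treatment period on the "date of ETV, if ETV occurs less than 42 days after treatment discontinuation", that is at most 41 days after. Counting back: 166 − 41 = Day 125, 169 − 41 = Day 128, 172 − 41 = Day 131. Week 18 is Day 127, so the widest window is stopping drug from about Week 18 on.
- The Schedule of Activities places Visit 801 at 6 to 8 weeks after the ETV so that 8 weeks have passed since the last dose. That implies an ETV 0 to 2 weeks after the last dose. An ETV on Day 166 or later then means a last dose on Day 166 − 14 = 152 or later. The Week 22 visit is Day 155 ± 3, that is Day 152 to 158. On this timing the exposed group is essentially those who had the last planned dose.

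**Step 3. Would such an ETV be placed at Week 24?** SAP 6.2 excludes ETV data from the MMRM only when they fall off the planned collection schedule for that variable, and adds: "However, the data will still be used in other analyses". Excluding only off-schedule ETVs implies that some ETVs fall on a planned visit. SLEDAI-2K is planned at Week 24. No visible sentence says whether an ETV in that window becomes the Week 24 value for SLEDAI-4.

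**Step 4. Size.** The plan's own figure first. Inputs: 70 per group (Protocol 9.2), rates 0.40 and 0.64 (SAP 6.1), two-sided alpha 0.05. With mean rate 0.52,

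z = [0.24√70 − 1.96√(2 × 0.52 × 0.48)] / √(0.40 × 0.60 + 0.64 × 0.36) = (2.008 − 1.385) / 0.686 = 0.909, so power is 81.8%. The stated figure of at least 80% is reproduced.

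Let f be the share of an arm in the differing cell. That arm's response rate rises by f, and the difference becomes 0.24 + f(active) − f(placebo). The documents give no value for f, so the values below are assumptions.

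| f | participants of 70 | difference, active arm only | difference, placebo only | power, placebo only |
|---|---|---|---|---|
| 1% | 0.7 | 25 points | 23 points | 78.4% |
| 2% | 1.4 | 26 points | 22 points | 74.7% |
| 3% | 2.1 | 27 points | 21 points | 70.6% |
| 5% | 3.5 | 29 points | 19 points | 61.9% |

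If both arms are affected equally, the difference stays 24 points and power is 81.9% to 82.5%. If no ETV is counted as Week 24, f = 0 and the two rules give the same responders.

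One way to build f is discontinuation share × share of those with an ETV counted as Week 24 × share of those with a 4-point drop. Assumed ranges of 10–20%, 10–30% and 40–60% give 0.10 × 0.10 × 0.40 = 0.4 points to 0.20 × 0.30 × 0.60 = 3.6 points. The middle factor presupposes that ETVs are counted at all, and the timing in Step 2 makes the low end more realistic.

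**The case against.** The strongest reply is that the SAP already gives the right answer. Criterion 1 asks for the reduction at Week 24; the SAP equates Week 24 with Visit 15 and, in 6.4, ties Visit 15 to those who completed treatment. A discontinuer has no Visit 15, so the value is missing and NRI makes it a nonresponse. The one visible rule that places unscheduled visits into by-visit analyses is confined to electronic patient-reported outcomes, and SLEDAI-2K is clinician-administered. Item carry-forward in Appendix 1 needs the visit to have occurred. This stands for most discontinuers. It does not make discontinuation part of the rule, and it does not settle an ETV that falls in the Week 24 window.

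Parts of the SAP are redacted, and 6.15 sends secondary derivations to a separate document. A visit-assignment rule may exist there. It could close the practical gap, but 6.5.1 would still contradict 4.1.

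A reader might infer more than the documents support:

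- That early stoppers in general count as responders. They do not; NRI catches those without a Week 24 value.
- That SAP 6.2 or the 42-day limit assigns ETVs to Week 24. The first concerns what stays out of the MMRM, and the second marks the end of the treatment period. Neither is a visit window.
- That Appendix 1 deletes the completion condition from BICLA and SRI-4. Appendix 1 also omits the medication rule, which 6.15 plainly applies; it derives the clinical instruments only, so its silence shows nothing.
- That injection site reactions tilt the result toward one arm. Protocol 2.3 calls them mainly low-grade, and no discontinuation rate is given.

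**Conclusion.** The contradiction holds on the text alone. SAP 6.5.1, 6.14 and 6.15 omit a condition that SAP 4.1 and three protocol sections require for the primary response. The practical consequence is narrow: it needs a late discontinuer, an ETV counted as Week 24, a drop of at least 4 points and no medication violation.

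The size cannot be read from the documents. It is probably small: at 1% to 3% of an arm it is about 1 to 2 participants of 70. It is zero if no ETV is counted as Week 24, and it biases the difference only to the extent that the arms are affected unequally. The direction is unknown. The planned power does not change once the rule is corrected. The case for acting is that the primary endpoint should have one definition, not that a large bias has been shown.

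**What to change.** Before unblinding:

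- In SAP 6.5.1, name permanent discontinuation of study drug before Week 24 as an intercurrent event under the composite strategy, and add its absence as a third responder criterion.
- Mirror this in 6.14 and 6.15 so that SRI-4, BICLA and LLDAS inherit it.
- State that ETV data from participants who discontinued are not counted as Week 24 responses for the composite endpoints.

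Appendix 1 need not change. The cost is a few lines of SAP text and one programming flag. No sample size or power figure is affected, and the result is the definition already in the protocol.

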6.5.2. Secondary Estimands

The secondary estimands for the secondary objectives are described by the following attributes:

- population: mITT population
- endpoints: SRI-4 at Week 24, BICLA at Week 24 (in the subset of participants with ≥ 1 A or ≥ 2 B at baseline), LLDAS at Week 24

- ICE will be accounted using the same estimand strategy as for the primary estimand (Section 6.5.1).
- population-level summary: difference in response rate of a secondary endpoint between LY3471851 and placebo
- rationale for estimand is provided in Section 6.5.1.

6.5.3. Supportive Estimand for Primary and Secondary Objectives

A supportive estimand for the primary and secondary objectives will be considered to address a clinical question: What is the difference between LY3471851 and placebo in the target patient population, in achieving successful response at Week 24 without regards to violation of concomitant medication rules?

For the supportive estimands, a **treatment policy estimand strategy** will be used to account for ICEs, and treatment effect will be assessed regardless of whether ICEs has occurred or not. That is, observed data after ICEs will be included as is in the analysis. Population, endpoints, and population-level summary are the same as described in Sections 6.5.1 and 6.5.2.

The image shows the letters 'CCI' in a large, bold, red serif font. The letters are set against a solid black rectangular background. The 'C' and 'I' have a classic, slightly ornate design, while the 'C' in the middle is a simple, clean serif. The overall appearance is that of a corporate or institutional logo.

6.6. Definition of Populations

The following populations are defined for this study:

Population	Description
Entered population	All participants who sign the informed consent form
Modified Intent-to-Treat (mITT) population	All participants randomly assigned to study intervention and who take at least 1 dose of study intervention. Participants will be analyzed according to the intervention to which they were assigned.
Per-Protocol (PP) population	All randomized patients who do not commit an Important Protocol Deviation (IPD) that could potentially compromise efficacy results. IPDs are specified in the Trial Issue Management Plan.
Safety population	All participants randomly assigned to study intervention and who take at least 1 dose of study intervention and did not discontinue the study for the reason “lost to follow-up” at the first postbaseline visit. Participants will be analyzed according to the intervention they actually received within each study period.
Pharmacokinetic (PK) Analysis population	All participants randomly assigned to study intervention and who take at least 1 dose of study intervention they actually received and have PK data available.

The mITT population will be used in analyses of efficacy and PRO, unless otherwise specified.

6.7. Participant Characteristics

6.7.1. Demographics and Baseline Characteristics

Demographics and baseline characteristics will be summarized using the mITT population by treatment group. The summary will include descriptive statistics such as the number of patients (n), mean, SD, median, min, and max for continuous measures, and frequency counts and percentages for categorical measures. No formal statistical comparisons will be made among treatment groups, unless otherwise stated.

The continuous demographic and baseline characteristic variables outlined in [Table KFAJ.6.1](#) will be summarized using descriptive statistics.

Table KFAJ.6.1. Continuous Demographic and Baseline Characteristic Variables

Variable	Quantitative	Categorical Summary	Subgroup Analysis
Demographic Characteristics			
Age ^a	Yes	<65, 65 to <75, ≥75	
Height	Yes		
Weight	Yes		
BMI ^b	Yes		
Sex	No	Female, Male	Yes
Race	No	American Indian/Alaska Native, Asian, Black/African American, Native Hawaiian or other Pacific Islander, White, or Multiple	Yes
Country		Canada, United States, Puerto Rico, Argentina, Mexico, Belgium, Czech Republic, France, Germany, Hungary, Italy, Poland, Romania, Spain, United Kingdom, South Korea, Taiwan, Japan, Australia, India, Israel, Russia, Ukraine	
Region (Table KFAJ.5.1)		North America, Latin America, Europe, Asia, Japan, Rest of World	Yes
Country GDP	No	Category 1 [Mexico, India, Ukraine] Category 2 [Argentina, Czech Republic, Hungary, Poland, Romania, Spain, Russia] Category 3 [Canada, United States, Puerto Rico, Belgium, France, Germany, Italy, United Kingdom, South Korea, Taiwan, Japan, Australia, Israel]	Yes
Ethnicity (only US sites)		Hispanic/Latino, Non-Hispanic/Non-Latino, Missing	Yes
Time since onset of lupus (years) ^c	Yes		
Concomitant Medication Use at Baseline			
Daily dose of prednisone (or equivalent) in mg/day ^d	Yes	<7.5 mg/day, ≥7.5 mg/day <10 mg/day, ≥10 mg/day	Yes
Immunosuppressant use	No	Yes, No	
Mycophenolate mofetil use	No		
Azathioprine use	No		
Methotrexate use	No		

Variable	Quantitative	Categorical Summary	Subgroup Analysis
Antimalarial use (for each drug)	No	Yes, No	
NSAID use	No		
Disease Severity at Baseline			
SLEDAI-2K	Yes	<10, ≥10	Yes
SLEDAI-2K organ system involvement at baseline	No	Yes, No	
British Isles Lupus Assessment Group (BILAG) organ system involvement at baseline (either A or B)	No	Yes, No	
BILAG A organ system involvement at baseline	No	Yes, No	Yes
CCI [REDACTED]	■	■	■
CCI [REDACTED]	■		
CCI [REDACTED]	■	■	■
CCI [REDACTED]	■	■	■
CCI [REDACTED]	Yes		
Physician's Global Assessment of Disease Activity score	Yes		
CCI [REDACTED]	■		
CCI [REDACTED]	■		
CCI [REDACTED]	■		

Variable	Quantitative	Categorical Summary	Subgroup Analysis
SLE Risk Probability Index (SLEPRI)	Yes	≤ 7 , 7 to ≤ 11 , 11 to ≤ 14 , > 14 (lower bounds are strictly greater than)	Yes
Prior Benlysta (belimumab) use	No	Yes, No	

Abbreviations: CCI; GDP = gross domestic product; NRS = numeric rating scale; NSAID = nonsteroidal anti-inflammatory drug; SLE = Systemic Lupus Erythematosus; SLEDAI-2K = Systemic Lupus Erythematosus Disease Activity Index 2000.

- a Age will be calculated using an imputed date of birth of July 1st in the year of birth collected in the electronic case report form (eCRF). It will be calculated as: $\text{Age (in years)} = (\text{date of first dose} - \text{imputed date of birth}) / 365.25$
- b Body mass index (BMI) (kg/m²) at Visit 2. $\text{BMI (kg/m}^2\text{)} = \text{Weight [kg]} / \text{Height [m]}^2$
- c Time since onset of lupus will be calculated using the date of onset of lupus (as recorded on the SLE History eCRF page) as follows: $\text{Time since onset of lupus (years)} = (\text{date of first dose} - \text{date of onset of lupus} + 1) / 365.25$.

CCI

- d Patients with a non-zero dose at Visit 2 will be included in this baseline summary, see Section 6.9.1 for details of prednisone (or equivalent) baseline dose.

